**Project Summary:**

The primary goal of this project is to compare the effectiveness of a family-centered approach to diabetes self-management resources (intervention) with the untailored approach of usual care. Diabetes self-management resources will be tailored to families' unique self-management barriers as identified by a 10-minute survey tool called PRISM (Problem Recognition in Illness Self-Management). Based upon the results of PRISM, families will receive self-management resources aligned to address their identified barriers. We will coordinate group-based delivery of the resources with routine diabetes clinic visits. These group-based resources will be delivered in four 75-minute sessions over a year. To assess the effectiveness of the intervention, we will examine glycemic control (A1c), fear of hypoglycemia, and quality of life for the child and parent.

**Background and Significance:**

Children with type 1 diabetes face complex self-management regimens, making adherence challenging and ultimately resulting in poor blood sugar control. Several common barriers interfere with diabetes control such as limited knowledge or challenges with staying motivated. In addition, both children and parents experience reduced quality of life, compared to those not living with diabetes. Efficacious strategies exist to improve diabetes self-management and quality of life, including but not limited to diabetes education or motivational interviewing. Patients and families often do not access these strategies, citing inconvenience of attending and lack of belief that the resource will help their specific issues.

To ensure resources do address each family's specific issues, a family-centered approach has been suggested. Family-centered care engages the family in the decision-making about the child's health and well-being, specifically around the types of information and support that the family may need to achieve better health outcomes. In this study we will take a family-centered approach to providing diabetes self-management by identifying families' unique self-management barriers through the 10-minute survey tool called PRISM.

We conducted a pilot study (n=65) of our intervention, focusing on two PRISM barrier domains, 1) Family Teamwork and 2) Understanding and Organizing Care. At the pilot's conclusion, 75% families in ADA-based Diabetes Education and 67% in Family Teamwork had completed the year-long trial, similar to rates in published trials. Although not powered to detect statistical significance, the participants receiving the PRISM-tailored self-management resources demonstrated a highly clinically significant mean 0.8-point reduction in A1c at the conclusion of the pilot study.

**Specific Aims:**

The aims of this three-year study are to improve glycemic control and quality of life (QOL) for children with type 1 diabetes and their parents. We hypothesize that families receiving the intervention (family-centered tailoring of diabetes self-management resources) will have improved glycemic control for their children and improved QOL for the child and parent.

## **Research Design and Method**

### **Study Population:**

The total number of subjects is 300 families (family being a child with type 1 diabetes and their parent).

### **Inclusion:**

1) Children ages 8 years to 16 years with type 1 diabetes and their parent/guardian; 2) Receive care at either the UW-Madison Pediatric Diabetes Clinic (UW) or the Pediatric Diabetes Care Program at Children's Hospital of Wisconsin (CHW); 3) Planning to continue care at their clinic site for the next 2 years; 4) Can speak and read English; 5) Diagnosed with type 1 diabetes for  $\geq 12$  months.

### **Exclusion:**

1) Newly diagnosed with type 1 diabetes ( $< 12$  months); 2) A subject in prior preliminary work for this study

### **Subject Identification and Recruitment:**

Recruitment for this study will occur in three ways: 1) in-person recruitment by research team members at the UW or CHW diabetes specialty clinics; 2) email or regular mail recruitment sent to UW or CHW diabetes clinic patients; and 3) flyers/notices at the diabetes clinics or on their websites.

For in person recruitment, a member of the healthcare team will approach a potentially eligible child and parent/guardian at their visit to ask if interested in learning about our study. If yes, the healthcare team member will notify the research assistant who will explain the study to the child and parent/guardian. At the onset of this discussion, research staff will verify that the adult accompanying the child is the parent/guardian. Following the study explanation, all parents who remain interested in participating will be asked 21 screening questions to determine basic eligibility. Identifiable information will not be collected with exception of contact information. However, all identifying data will be removed if parents are not eligible or decide not to participate in the study. This screening is either in paper form or via secure UW Qualtrics application.

For those families who remain eligible after the basic screener, research staff will provide the parent/guardian as well as the child with the appropriate age-based consent/assent form and allow sufficient time for them to read it. As documented in detail in the application, standard IRB-recommended consent processes will be followed, including adherence to age-based recommendations for consent/assent.

For recruitment of current patients, we will send information about the study and an invitation to complete the basic eligibility screen either electronically (for those at UW who have previously provided consent to be contacted with research opportunities) or via US mail. The letter will contain the study information sheet and a secure link to UW Qualtrics link where they can complete the screening questions to determine basic eligibility. Those who do not have internet access can complete a paper copy of the

basic eligibility screener and return with a postage paid envelope, provided in our mailer.

With regard to flyers and notices, we will have a recruitment flyer to post in the clinic sites and on clinic websites. The flyer will provide contact phone numbers through which parents can request study information through email or regular mail. The research coordinator will get permission from the clinic administrator or web host to post the flyer.

**Study Activities:**

Screening for eligibility takes place at or up to 6 weeks before baseline data collection. Once determined to be eligible and informed consent is obtained, data collection elements and time points for usual care (U) and intervention (I) subjects proceed as in the timeline below.

Data collection for usual care (U) and intervention (I) groups							
Data Element	Baseline (0 months)	Session 1 (3 months)	Session 2 (6 months)	Session 3 (9 months)	Session 4 (12 months)	6 month post (18 months)	12 month post (24 months)
Glycemic control							
A1c	U, I	U, I	U, I	U, I	U, I	U, I	U, I
Fear of hypoglycemia	U, I		U, I		U, I	U, I	U, I
QOL							
Parent	U, I		U, I		U, I	U, I	U, I
Child	U, I		U, I		U, I	U, I	U, I
PRISM	U, I		U, I		U, I	U, I	U, I
Covariates							
Family characteristics	U, I				U, I		U, I
Disease and regimen factors	U, I				U, I		U, I

The first outcome of interest is *glycemic control*, measured by A1c and fear of hypoglycemia. A1c is routinely obtained during clinic visits by point of care A1c. This outcome measure is continuous, but values could also be used to understand whether diabetes control is adequate (A1c values meets American Diabetes Association criteria). Fear of hypoglycemia will be assessed with standard tools for the parent and the child (15 items, survey burden 3 minutes), when age-appropriate. The second main outcome of interest is *QOL*, for both the parent and the child. The child and parent will complete these survey items (survey burden 10 minutes). For the child, we will assess diabetes-specific QOL, measured by the total scale score (33 questions). Although prior work with this instrument suggests children as young as 7 years can complete the survey unassisted, research staff will be available to read the questions to younger children as needed. We will supplement these measures with published items assessing school, work, and play activities (9 questions). For the parent, the adult version of the Peds QL™ Family Impact Module (28 questions) will be used (e.g., impact of diabetes on daily household and work activities, family relationships, and social functioning).

Surveys will also periodically assess change in barrier scores from the PRISM, as well as covariates such as demographics (e.g., child gender or household composition),

healthcare utilization (e.g., hospitalizations or provider visit type and date), comorbidities, and insulin regimen (e.g., pump or injection).

### **Information from Medical Records:**

Families will be asked for consent to collect information from the child's medical record. This information would include demographics (e.g., gender, date of birth, zip code, or insurance provider), growth parameters (e.g., height and weight), healthcare utilization data (e.g., hospitalizations, healthcare provider visits, and names of providers), other comorbidities (e.g., celiac disease) and date of diagnosis, referrals to providers/resources (e.g., the diabetes educator or eye care), and insulin regimens, as well as lab orders and results (e.g., hemoglobin A1c, thyroid screening, urine screening, blood pressure, cholesterol, or celiac screening).

### **Data Collection:**

We will screen possible participants to determine if they meet inclusion criteria. Once basic eligibility is determined and informed consent is obtained, we will administer a survey including the PRISM (Problem Recognition in Illness Self-Management) tool, as well as family characteristics, quality of life, fear of hypoglycemia, and disease management factors (for example, regimen and adherence). Family characteristics include parent/child age (continuous), race/ethnicity, child gender, parent relationship to the child (mother, father, or other) and household structure (single parent, two parent, or other), parent education (standard categories), primary diabetes provider, distance to care, disease and regimen factors including year of diagnosis, insulin regimen, and use of glucose monitoring technology, lifetime number of diabetes hospital days and hospitalizations, inventory of specific chronic illnesses (e.g., attention deficit/hyperactivity disorder, developmental delay, celiac disease, or asthma), and health status (single item, 5-point scale).

### **Statistical Considerations:**

A first step in our analyses is the description of our data. Bivariate relationships will be assessed with measures of association such as correlations and regression coefficients for continuous variables and odds ratios for categorical variables. Ordinal and count variables will be collapsed into fewer categories if some levels are sparsely populated. We will undertake a full analysis of the level, reason, and impact of missingness. Several techniques will be applied to assess whether bias from missing data has occurred. These include multiple imputation of missing data elements and pattern mixture models to assess the impact of missed visits.

Analyses will model intervention outcomes with mixed effects models as:

$$g(y_{ft}) = (\beta_0 + a_f) + \beta_1(Intervention)_{ft} + (\beta_2 + b_f)(time)_{ft} + \beta_3(Intervention \times time)_{ft} + \varepsilon_{ft} \quad (\text{Equation 1})$$

where  $g$  is a link function suitable to producing appropriate measures of the intervention's effect for the scale of the outcome  $y$ ,  $t$  = time ( $t=0$ - $X$  time points during or after the intervention),  $f$  = family ( $f=1 \dots 300$  families),  $a_f$  and  $b_f$  are family specific random intercepts and slopes and  $\varepsilon_{ft}$  enters when equation 1 describes a mixed linear model.

The link function  $g$  will be chosen as the identity link for continuous outcomes (e.g., A1c), as the log for count variables, and as the logit for dichotomous variables. Time will be modeled in several ways: as indicator variables, as a pre-post intervention indicator, and as an ordinal indicator. Depending on results of these tests, the interventions' effect will be described for time points combined, as a trend, or at specific time points after initiation. The variance of random slopes and intercepts will be estimated to assess individual variation in time trends.

Covariates will be added to this model to increase precision and/or adjust for any imbalance between intervention arms as needed and will include an indicator for provider and family demographics. We will evaluate adding fixed effects for the site, although it is unlikely that this will significantly improve model fit as there is typically more variation between providers than between sites. All models will be constructed using Stata 12 (StataCorp, College Station, TX).

The study is powered to evaluate effects on glycemic control and quality of life (QOL), assuming a two-tailed  $\alpha=0.05$ . We conservatively estimated values over time for an individual family would correlate at 0.08. Previous studies suggest moderate effect sizes (0.3-0.50; e.g., 0.-1.0% reductions in A1c or 6-9 point improvements in QOL) for the self-management resources used in this trial. Using a repeated measures approach and considering our outcomes as continuous, samples of 100 families per arm will provide 80% power to detect small to moderate effects (0.2-0.30) on glycemic control and QOL. Power calculations were conducted with PASS 2008. Based on pilot data, we estimate 70% retention of subjects in the trial. Thus, we will recruit 300 families.

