Statistical Analysis Plan

Official Title: Family-Centered Tailoring of Pediatric Diabetes Self-Management Resources

NCT Identifier: NCT02024750

Date: 11/22/2017

Data Source

Children aged 8-16 years were recruited from 2 large multidisciplinary diabetes clinics serving both urban and rural populations. We collected A1c data at routine diabetes clinic visits at 9 time points (quarterly during the intervention and for a year after the intervention). Quality of life (QOL) data were collected from parents and children at 5 time points: at baseline, at 3 months after the first intervention session, and at 3, 6, and 9 months after the intervention ended. Fear of Hypoglycemia data were collected from parents at 4 time points: at baseline, at 3 months after the first intervention session, and at 3 and 9 months after the intervention ended.

Analysis Objectives

Applying an intention to treat approach, the primary hypothesis was that outcome trajectories differ between the intervention and usual care arms.

Outcomes

Primary outcomes were trends in A1c for the child, as well as child and parent quality of life. Trend in fear of hypoglycemia was a secondary outcome.

Handling of Missing Values and Other Data Conventions

Rates of missingness were low. Mixed effects regression models were fit via maximum likelihood and were hence robust to non-informative missingness. The influence of informative missing data was evaluated via pattern mixture models. Our evaluations indicated that missing data have no substantial impact on the results of our analyses, so we report results without imputing or modeling missing data.

Statistical Procedures

The primary analytic technique was mixed effects models with repeated measures to capture time trends in intervention and usual care groups via linear terms. Intervention effect was tested via interaction terms between treatment group and time trend, as initially proposed. Trajectories were fit for child's A1c and for QOL for child and parents, as well as fear of hypoglycemia. Preliminary analyses indicated that trajectories differed

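### The power paragraph calls a correlation of 0.08 conservative and claims 80% power for 0.2-0.30 without naming the contrast; on most contrasts that the Protocol lists, one of these two statements fails

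*Protocol*

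**What the plan says.** The power paragraph in the Protocol (Statistical Considerations) uses a two-sided 0.05 level. Its correlation input reads "We conservatively estimated values over time for an individual family would correlate at 0.08" and its result is that "samples of 100 families per arm will provide 80% power to detect small to moderate effects (0.2-0.30) on glycemic control and QOL". The expected effect is given as "Previous studies suggest moderate effect sizes (0.3-0.50; e.g., 0.-1.0% reductions in A1c or 6-9 point improvements in QOL", where the lower A1c figure is damaged. The method is described only as repeated measures with continuous outcomes, run in PASS 2008. With 70% retention, 300 families are to be recruited.

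Equation 1 in the same section has arm, time and arm-by-time terms with family random intercepts and slopes. The contrast is left open: "Time will be modeled in several ways: as indicator variables, as a pre-post intervention indicator, and as an ordinal indicator", and the intervention's "effect will be described for time points combined, as a trend, or at specific time points after initiation".

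The Study Activities table schedules A1c at months 0, 3, 6, 9, 12, 18 and 24, and QOL at months 0, 6, 12, 18 and 24.

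The SAP (Statistical Procedures) states: "Intervention effect was tested via interaction terms between treatment group and time trend, as initially proposed". For A1c its Data Source section gives a different schedule: "We collected A1c data at routine diabetes clinic visits at 9 time points".

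**The concern.** A correlation between repeated measurements has no fixed direction of caution. When each family's visits are averaged, a higher correlation makes the visits more redundant and raises the detectable effect, so a low assumed value is optimistic. When change over time is compared, a higher correlation cancels more between-family variation and lowers the detectable effect, so a low value is cautious. A paragraph that calls 0.08 conservative without naming the contrast cannot be checked as written.

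The paragraph is the only stated basis for 100 families per arm and 300 recruited. If the claim belongs to a time-averaged comparison, it does not describe the test that the SAP reports. If it belongs to that test, the reader needs to know at what time point 0.2-0.30 is measured.

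**Working it through.** **Inputs from the documents.** Two-sided 0.05 and 80% power, so z = 1.960 + 0.842 = 2.802; n = 100 per arm; correlation ρ = 0.08; the Protocol's visit months.

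**Assumptions.** Effects are in SD units; compound symmetry; no random-slope variance. The documents give no correlation other than 0.08, so 0.5 and 0.8 are illustrations.

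**Step 1: reproduce the stated range (time-averaged, m visits).** Detectable effect = z × √[(2/n) × (1 + (m−1)ρ)/m].
- m = 2: 2.802 × √(0.02 × 0.540) = 0.291
- m = 5: 2.802 × √(0.02 × 0.264) = 0.204
- m = 7: 2.802 × √(0.02 × 0.2114) = 0.182

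So 0.08 matches the lower end with the scheduled 5-7 visits. The upper end needs only two measurements.

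**Step 2: arm-by-time slope, read at month T.** Detectable effect = z × T × √[(2/n) × (1−ρ)/Sxx], where Sxx is the sum of squared deviations of the visit months from their mean.
- A1c: Sxx = 1170 − 72²/7 = 429.4. At month 24: 2.802 × 24 × √(0.02 × 0.92/429.4) = 0.440
- QOL: Sxx = 144 + 36 + 0 + 36 + 144 = 360. At month 24: 2.802 × 24 × √(0.02 × 0.92/360) = 0.481

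The standard errors of the month-24 difference are 0.157 and 0.172. Power at 0.30 is Φ(0.30/0.157 − 1.960) = 48% for A1c and Φ(0.30/0.172 − 1.960) = 42% for QOL. At 0.50, the top of the expected range, it is 89% and 83%.

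**Step 3: direction of the correlation (100 per arm).**

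| ρ | Time-averaged, 5 / 7 visits | Slope at month 24, A1c / QOL | Slope at month 12, A1c / QOL |
|---|---|---|---|
| 0.08 | 0.204 / 0.182 | 0.440 / 0.481 | 0.220 / 0.240 |
| 0.5 | 0.307 / 0.300 | 0.324 / 0.354 | 0.162 / 0.177 |
| 0.8 | 0.363 / 0.361 | 0.205 / 0.224 | 0.103 / 0.112 |

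**Step 4: the other contrasts the Protocol lists.**
- One specific visit: 2.802 × √0.02 = 0.396, whatever the correlation.
- Baseline against the mean of r later visits: z × √[(2/n) × ((1 + (r−1)ρ)/r + 1 − 2ρ)]. At ρ = 0.08 this is 0.425 (r = 4) and 0.410 (r = 6).

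Neither reaches 0.30.

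**Step 5: readings that reconcile the paragraph.** Take one straight slope over 24 months at ρ = 0.08.
- Month 12: 0.220 (A1c) and 0.240 (QOL).
- Average over post-baseline visits: the mean month is 72/6 = 12 for A1c, giving 0.220, and 60/4 = 15 for QOL, giving 15/24 × 0.481 = 0.300.

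**Step 6: supplementary figures at ρ = 0.08.**
- 150 per arm (assumes 1:1 allocation and all 300 families contributing): month-24 values 0.36 (A1c) and 0.39 (QOL); power at 0.30 is 65% and 57%.
- Adding a between-family slope SD of 0.5 SD over 24 months (assumed), 100 per arm: 2.802 × √[0.02 × (0.92 × 576/Sxx + 0.25)] = 0.48 and 0.52.
- SAP visits, single slope, 100 per arm: 0.39 at month 24 for A1c (nine quarterly visits). For QOL, with times read as months 0, 6, 15, 18 and 21, it is 0.46 at month 21 and 0.52 if extrapolated to month 24.
- Separate slopes during and after the intervention (knot at month 12, assumed), Protocol visits: the during-intervention slope detects 0.46 (A1c) and 0.51 (QOL) at month 12.

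The retention arithmetic is sound: 200/0.70 = 286, consistent with recruiting 300.

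**The case against.** The best defence is that no figure is proved wrong. Month 12 is the last intervention session and a natural time to quote an effect. On a single slope 0.08 then gives 0.22 and 0.24, and a low correlation is indeed conservative. The post-baseline average, at 0.22 and 0.30, matches the stated range almost exactly. This stands as a possible reading. But neither document states that scale, and it requires the arms to keep diverging at the same rate for a year after the last session, reaching 0.44 and 0.48 SD at month 24.

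A baseline-adjusted mean of the later visits would also give 0.19-0.22 at 0.08 (0.23-0.24 at 0.5, 0.17-0.18 at 0.8). There 0.08 is cautious only against high correlations, and the Protocol does not list this contrast.

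Powering a time-averaged comparison would also be legitimate, because the Protocol allows time points to be combined. In that case only the word conservatively is wrong.

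The printed 0.08 may itself be a typing or PDF-reading fault, since the same paragraph has a damaged A1c figure. At 0.8, used only as an illustration, the month-24 values are 0.21 and 0.22, inside the stated range.

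A reader might infer that the trial's test could detect only 0.39-0.52 SD and that the trial was underpowered. The documents do not support that. Both ends of that range use SAP visit times, which are not those of the Protocol's table, and the upper end extrapolates QOL past its inferred last visit. The two-slope model followed preliminary analyses, so the power paragraph could not have targeted it. Nor can one argue at the same time that the true correlation is well above 0.08 and that the slope test falls short because it is 0.08.

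**Conclusion.** The point holds as a specification and reporting fault. The correlation, its description as conservative and the 0.2-0.30 claim cannot all be read together on most of the contrasts the Protocol lists. With time points combined, the description runs the wrong way. For a single visit, a pre-post change or a slope read at month 24, the range is not reached at 0.08.

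The shortfall for the slope test is conditional on the printed 0.08, the month-24 scale, compound symmetry and the Protocol's visits. Leaving out random-slope variance favours the plan, since both models include random slopes. The size of that variance is unknown, and so is the number of families analysed.

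The practical effect is on how the stated power is understood. Even on the month-24 reading, power is above 80% for an effect of 0.50. The SAP is written in the past tense, so the correction concerns a stated figure and its input, not the design. It is worth making because it is cheap and the paragraph is the sample size justification. Confidence is medium, because the PASS output would settle which statement is at fault.

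**What to change.** 1. Check 0.08 against the PASS output and correct it if it is a misprint. Repair the damaged A1c figure at the same time.
2. State the contrast powered, the visits used, the covariance structure and the time point or average to which 0.2-0.30 refers.
3. Delete the word conservatively unless it is true for that contrast.
4. Restate the detectable effect for the arm-by-time test, separately for A1c and QOL, over a range of correlations and at both time points. Possible wording: *With 100 families per arm, two-sided 0.05, 80% power, compound symmetry and no random-slope variance, a single arm-by-time slope over 24 months detects a month-24 (month-12) difference of 0.44 (0.22) SD for A1c at seven visits and 0.48 (0.24) SD for QOL at five visits if the correlation is 0.08; 0.32 (0.16) and 0.35 (0.18) at 0.5; and 0.21 (0.10) and 0.22 (0.11) at 0.8. Random-slope variance makes these values larger.*
5. Give figures for the SAP visits and the two-slope model only as supplementary, labelled as later than the power calculation.

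The cost is one paragraph and a recalculation, with no change in enrolment. The downside is that, if 0.08 is correct, the stated detectable effect for the slope test may become less favourable.
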